4.2. Protocol Deviations

Potential deviations will be identified and documented prior to database lock. Protocol deviations will be derived from the eCRF data, electronic vendor data, and will be obtained from the clinical monitoring reports. All deviations from these sources will be reconciled and duplicate deviations will be removed.

Possible deviations include, but are not restricted to the following deviation types:

- Ineligible subject/study entry criteria not satisfied.
- Informed consent not completed correctly.
- Non-compliance with study treatment.
- Prohibited medications/procedure.
- Visit/procedure missing or out of window.
- The Endo study team will approve all final protocol deviation assignments and classify them as either major or minor during ongoing protocol deviation review meetings, with the final meeting held prior to the database lock.

4.3. Prior/Concomitant Medications and Procedures

All medications will be coded using the World Health Organization (WHO) Drug Dictionary by active ingredient and anatomical therapeutic chemical (ATC) classification of ingredients. The dictionary version used is defined in the Data Management Plan.

Any medications/procedures within 90 days prior to the Screening Visit will be classified as prior medications/procedures.

Any medications/procedures from the Screening Visit through the Day 265 Visit will be classified as concomitant medications/procedures.

4.4. Prior EFP Treatment

Prior EFP treatment will be obtained from the prior/concomitant medication and/or prior/concomitant procedure pages of the eCRF. If on either of these pages a medication or procedure is reported with the indication ‘EFP/Cellulite’ and the start date is prior to the Screening Visit, then the medication or procedure will be considered a prior EFP treatment.

All medications will be classified as EFP Drug. All procedures will be classified into one of the following groups:

- Liposuction.
- Laser.
- Massage.
- Radiofrequency.
- Mesotherapy.
- Cream.

- Other.

The classification will be reviewed and approved by the study medical monitor. Any EFP treatment used after the Day 1 visit will be noted and reported as a protocol violation.

4.5. Efficacy Parameters

Cellulite assessments using the PR-PCSS, CR-PCSS and Hexsel CSS will be performed at Screening, Days 22, 43, 71, 161, and 251.

4.5.1. Change from Baseline in PR-PCSS Rating (Primary Endpoint)

To assess the subject reported impact of CCH in the treatment of cellulite in adult females, the change from Baseline (Screening) in PR-PCSS will be determined for treatment region (both buttocks or both thighs) on Day 71.

4.5.2. Change from Baseline in PR-PCSS Rating (Secondary Endpoint)

To assess the subject reported impact of CCH in the treatment of cellulite in adult females, the change from Baseline (Screening) in PR-PCSS will be determined for treatment region (both buttocks or both thighs) on Days 22 and 43.

4.5.3. Change from Baseline in CR-PCSS Rating (Secondary Endpoint)

To assess the clinician reported impact of CCH in the treatment of cellulite in adult females, the change from Baseline (Screening) in CR-PCSS will be determined for treatment region (both buttocks or both thighs) on Days 22, 43, and 71.

4.5.4. Change from Baseline in Hexsel CSS Total Score (Secondary Endpoint)

To assess the clinician reported impact of CCH in the treatment of cellulite in adult females, the change from Baseline (Screening) in Hexsel CSS total score will be determined for treatment region (both buttocks or both thighs) on Days 22, 43, and 71.

4.5.5. Proportion of Subjects with No Change (or Worsening) from Baseline (Tertiary Endpoints)

Complete loss of Response at Days 161 and 251 is defined as worsening of cellulite severity improvement on PR-PCSS/CR-PCSS /Hexsel CSS total score ratings at Days 161 and 251 compared to the score at Day 71, where cellulite severity returns to baseline levels or worse.

Tertiary endpoints will be analyzed for each scale separately.

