3. OBJECTIVES AND ENDPOINTS

Objectives	Endpoints
Primary	

 To assess the subject reported impact of CCH in the treatment of cellulite in adult females. 	
 The change from baseline (screening) in Patient Reported Photometric Cellulite Severity Scale (PR-PCSS) at Day 71.
Secondary	

 To assess the subject and clinician reported impact of CCH in the treatment of cellulite in adult females. 	
 The change from baseline (screening) in PR-PCSS at Days 22 and 43. The change from baseline (screening) in Clinician-reported Photometric Cellulite Severity Scale (CR-PCSS) at Days 22, 43, and 71. The change from baseline (screening) in Hexsel Cellulite Severity Scale (CSS) at Days 22, 43, and 71.

 To radiologically assess the impact of treatment with CCH in adult females with cellulite. 	
 Comparison of baseline (screening) MRI tissue morphology and septae under the treatment areas to images taken at Day 71.

 To evaluate tissue histopathology to assess the impact of treatment with CCH in adult females with cellulite. 	
 Comparison of baseline (screening) histopathology to the histopathology of samples taken at Day 71.

 To assess the safety of CCH treatment of cellulite in adult females. 	
 The proportion of subjects reporting each AE, treatment-emergent adverse event (TEAE), adverse event of special interest (AESI), and serious adverse event (SAE). The change from baseline in vital signs and clinical laboratory parameters at each visit where these parameters are measured. The change from baseline in anti-AUX-I and anti-AUX-II antibodies and neutralizing antibodies at each visit where these parameters are measured.
Tertiary	

 To assess the complete loss of patient reported impact after CCH treatment in adult females with cellulite. 	
 The proportion of subjects with no change (or worsening) from baseline (screening) in PR-PCSS rating at Day 161 and at Day 251.

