
 To assess the complete loss of clinician reported impact after CCH treatment in adult females with cellulite. 	
 The proportion of subjects with no change (or worsening) from baseline (screening) in CR-PCSS rating at Day 161 and at Day 251. The proportion of subjects with no change (or worsening) from baseline (screening) in Hexsel CSS total score at Day 161 and at Day 251.

 To radiologically assess the long-term impact of treatment with CCH in adult females with cellulite. 	
 Comparison of baseline (screening) MRI tissue morphology and septae under the treatment areas to images taken at Day 251.

 To evaluate tissue histopathology to assess the long-term impact of treatment with CCH in adult females with cellulite. 	
 Comparison of baseline (screening) histopathology to the histopathology of samples taken at Day 251.

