6.2. Derived Variables

Refer to Table 12 below for derived variables and their definitions for various study parameters.

Table 12: Derived Variables and Definition

Variable	Definition
Height (cm)	If height is recorded in inches, then height is equal to the recorded value multiplied by 2.54 and then rounded to 1 decimal place.
Weight (kg)	If weight is recorded in pounds, then weight is equal to the recorded value multiplied by 0.454 and then rounded to 1 decimal place.
Baseline	Baseline is defined as the last non-missing measurement/assessment prior to the CCH injections given at Day 1. Any assessments performed at an unscheduled visit will be considered in the calculation of baseline, if the unscheduled assessment is the closest value preceding the study drug injection.
Study Day	Study Day will be computed as Date of Assessment – Date of Day 1 + 1 for assessments on or after Day 1, else study day will be computed as Date of Assessment – Date of Day 1.
Change from Baseline	Change from baseline will be derived as post-baseline visit/time point value – the baseline value.
Last Date in the Study	Last date in study is defined as: 
 • The date of Day 265 (Biopsy follow-up visit) if the subject completes the study • The date of early termination visit if the subject is terminated early from study at a non-scheduled visit • The date of the latest scheduled visit if the subject is terminated early from study at a scheduled visit or lost to follow-up.
Age (Years) at EFP Symptom Onset	Date of EFP symptoms reported – Date of Birth/365.25. See Section 6.3.1.3 for handling of partial or unknown EFP symptom onset dates.
Time (Years) Since Last EFP Treatment	Date of most recent EFP treatment – Date of informed consent/365.25. See Section 6.3.1.3 for handling of partial or unknown EFP treatment dates.
Duration (Minutes) of Exposure at Each Visit	Date/Time of Last Injection – Date/Time of First Injection
Duration of AE(Days)	AE end date – AE start date + 1
AE Onset Day	AE start date – Date of Day 1 + 1.

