7.6.1. Primary Endpoint

7.6.1.1. Change from Baseline in PR-PCSS Rating at Day 71

The baseline PR-PCSS ratings and the level of change in PR-PCSS ratings from Baseline (Screening) at Day 71 will be summarized using frequency counts and percentages for each severity rating and with mean and SD.

To assess the impact of CCH at Day 71, the PR-PCSS ratings at Day 71 will be compared with Baseline ratings using paired *t* test. The normality assumption of the difference of assessment will be evaluated using Shapiro-Wilk test and Q-Q plot.

Two-sided *p* value with 5% level of significance will be used to check if normality is achieved or not. Normality will be concluded if the *p* value > 0.05.

In case normality assumption is not met then Wilcoxon Signed Rank Pratt Lehmann test (adjusted for the correction factor for ties and zeros, if present) will be used.

The result of the analysis will be presented as:

SAS appendix will be presented detailing the test of normality of differences in Day 71 and Baseline PR-PCSS ratings.

Paired *t* test: Mean difference between Baseline and Day 71 ratings and associated 95% CI, SE, and *p* value. The negative mean difference indicates improvement in cellulite severity at Day 71.

Wilcoxon Signed Rank Pratt Lehmann test: Sum of positive ranks, sum of negative ranks and *p* value will be presented. If the sum of the negative rank is greater than the sum of positive rank, then it indicates improvement in cellulite severity at Day 71.

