7.6.3. Tertiary Endpoints

7.6.3.1. Proportion of Subjects with No Change (or Worsening) from Baseline in PR-PCSS Rating on Days 161 and 251

The proportion of subjects with complete loss of response as provided in Section [4.5.5](#) in PR-PCSS rating will be summarized using frequency counts and percentages.

7.6.3.2. Proportion of Subjects with No Change (or Worsening) from Baseline in CR-PCSS Rating on Days 161 and 251

The proportion of subjects with complete loss of response as provided in Section [4.5.5](#) in CR-PCSS rating will be summarized using frequency counts and percentages.

7.6.3.3. Proportion of Subjects with No Change (or Worsening) from Baseline in Hexsel CSS Total Score on Days 161 and 251

The proportion of subjects with complete loss of response as provided in Section [4.5.5](#) in Hexsel CSS total score will be summarized using frequency counts and percentages.

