8. CHANGE FROM PROTOCOL

This SAP is prepared primarily based on the study protocol; original version dated October 22, 2019 and protocol amendment 1 dated January 16, 2020.

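### The SAP's tertiary tables would report loss of a Day 71 response under the title of a different endpoint, no change or worsening from baseline

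*SAP*

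**What the plan says.** Protocol section 3 gives the first tertiary endpoint as "The proportion of subjects with no change (or worsening) from baseline (screening) in PR-PCSS rating at Day 161 and at Day 251". The CR-PCSS and Hexsel endpoints are worded the same way. SAP Table 1 repeats all three, for example "The proportion of subjects with no change (or worsening) from baseline (screening) in Hexsel CSS total score at Day 161 and at Day 251". Each compares the late visit with baseline only.

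SAP 4.5.5 carries the same title but defines something called complete loss of response: a worsening of earlier improvement, judged on "ratings at Days 161 and 251 compared to the score at Day 71, where cellulite severity returns to baseline levels or worse".

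SAP 7.6.3 joins the two. Its first subsection is headed "Proportion of Subjects with No Change (or Worsening) from Baseline in PR-PCSS Rating on Days 161 and 251", yet the statistic under that heading is "The proportion of subjects with complete loss of response as provided in Section" 4.5.5. The CR-PCSS and Hexsel subsections follow the same pattern.

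SAP section 8, the place for departures from the protocol, says only: "This SAP is prepared primarily based on the study protocol; original version dated October 22, 2019 and protocol amendment 1 dated January 16, 2020". It lists no change to these endpoints.

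**The concern.** One title covers two different quantities. The endpoint as written asks how many subjects are no better than at baseline, whatever the reason. SAP 4.5.5 asks how many improved by Day 71 and then lost that improvement. Because 7.6.3 points to 4.5.5, only the second figure is planned, and it would be printed under the name of the first. A reader would take it for the protocol endpoint although subjects who never improved are left out of the count.

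The denominator is also unstated in 4.5.5 and 7.6.3. If the general rules in SAP 5, 6.1 and 7.6 apply, it is all Evaluable subjects or those with a rating at the visit. Subjects with no response to lose would then stay in the denominator and dilute the loss rate.

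The endpoint as written is not tabulated elsewhere in the SAP text. The other efficacy summaries in 7.6.1 and 7.6.2 stop at Day 71, so it could be recovered only from the individual rating listings promised in 7.6.

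**Working it through.** The documents give no planned rate for this endpoint, so there is no figure to reproduce. The check has two parts.

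**1. Which rating paths count under each rule**

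Write B for the baseline rating, D for Day 71 and L for the late visit (Day 161 or 251), on the 0 to 4 scale.

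- Endpoint as written: L ≥ B.
- SAP 4.5.5, plain reading: D < B and L ≥ B.
- SAP 4.5.5, loose reading that drops the need for earlier improvement: L > D and L ≥ B.

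For B = 3 or 4 there are 2 × 5 × 5 = 50 paths. (This restriction is illustrative: the entry criterion of 3 or 4 applies to the CR-PCSS, not the PR-PCSS.)

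| Rule | B = 3 | B = 4 | Total |
|---|---|---|---|
| As written | 5 × 2 = 10 | 5 × 1 = 5 | 15 |
| 4.5.5, plain | 3 × 2 = 6 | 4 × 1 = 4 | 10 |
| 4.5.5, loose | 6 + 1 = 7 | 4 | 11 |

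The one extra path under the loose reading is 3, 3, 4. The path 3, 3, 3 meets the endpoint as written and neither reading of 4.5.5. Both SAP rules contain L ≥ B, so no path meets 4.5.5 without meeting the endpoint. The SAP count can only equal it or fall below it.

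**2. Illustrative size**

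Assume one treatment area and 6 subjects in the region (SAP 3.3; the 3 moderate plus 3 severe per region in Protocol 6.1 gives the same number). Let k subjects be improved at Day 71, 1 of them back at baseline at the late visit, and j of the 6 − k non-improvers improve later. The values of k and j and the single loss are assumptions.

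- Endpoint as written = (6 − k − j + 1)/6
- SAP 4.5.5 count over all subjects = 1/6
- Loss among Day 71 improvers = 1/k

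With j = 0:

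| k | As written | 4.5.5 over all 6 | Among improvers |
|---|---|---|---|
| 3 | 4/6 = 67% | 1/6 = 17% | 1/3 = 33% |
| 4 | 3/6 = 50% | 1/6 = 17% | 1/4 = 25% |
| 5 | 2/6 = 33% | 1/6 = 17% | 1/5 = 20% |
| 6 | 1/6 = 17% | 1/6 = 17% | 1/6 = 17% |

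Late improvement narrows the gap. With k = 3, the endpoint as written falls from 67% to 50%, 33% and 17% as j goes from 0 to 1, 2 and 3. The difference from the SAP figure thus runs from 50 percentage points down to 0.

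**The case against.** The best defence of 4.5.5 is the objective. Protocol section 3 and SAP Table 1 attach these endpoints to the aim of assessing complete loss of impact, and a loss presupposes a gain. On that view the SAP is making the objective operational, and the tension already lies in the protocol, between objective and endpoint. This explains why 4.5.5 was written and is a good reason to keep the measure. It does not justify printing it under the other endpoint's title or leaving section 8 silent.

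Version drift is not the explanation either. The SAP was written on Amendment 1 and the current protocol is Amendment 3, but SAP Table 1 itself carries the baseline-only wording, so the SAP disagrees with itself.

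Other points have some force:

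- 4.5.5 is loosely worded, and on the loose reading a 3, 3, 4 subject would count without having improved. That reading ignores the word improvement in the definition, and a 3, 3, 3 subject is still excluded.
- The table layouts are in SAP Module 2, which is not among the documents at hand and may settle the denominator. The statement about dilution is therefore an inference.
- The percentages rest wholly on assumed counts, and the range includes no difference.
- The practical effect is small. The ratings are listed by subject, and with about 12 subjects the endpoint as written can be tallied by hand. The interim decision rests on MRI and biopsy, not on these scales.

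**Conclusion.** The concern holds. Followed exactly, SAP 7.6.3 produces a figure that is not the endpoint named in its headings, in SAP Table 1 or in the protocol, and the change is unrecorded. That follows from the texts alone and needs no assumption.

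The size depends on how many subjects fail to improve by Day 71. In the illustration the shortfall lies between 0 and 50 percentage points, given 6 subjects in a region, at least 3 improved at Day 71 and exactly 1 loss. The dilution of the loss rate further assumes that the SAP's general denominators apply.

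The severity is minor: the endpoint is tertiary and descriptive, and no test or decision depends on it.

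**What to change.** In SAP 4.5.5 and 7.6.3, report two separately named lines for each scale, visit, treatment area and region:

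1. **Protocol endpoint as written.** N = Evaluable subjects with non-missing baseline and visit ratings; n = those at or above baseline at the visit.
2. **Loss of response.** N = Evaluable subjects below baseline at Day 71 with a non-missing visit rating; n = those at or above baseline at the visit.

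Subjects not improved at Day 71 then count only in line 1. Name the Evaluable definition used, since Protocol 9.2 restricts it to subjects first dosed after 18 March 2020 and SAP section 5 does not.

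State what counts as improvement at Day 71. The SAP gives only a direction: "Change from baseline will be derived as post-baseline visit/time point value" minus baseline, and for the paired comparison "The negative mean difference indicates improvement in cellulite severity at Day 71". It sets no threshold for a single subject. On the Hexsel total (5 items scored 0 to 3, so 0 to 15) a 1-point fall would count unless the SAP says otherwise.

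Show the numbers of Day 71 non-improvers and of missing Day 71 ratings, and record line 2 in SAP section 8. The protocol endpoint can stay as it is.

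The cost is SAP wording and matching edits to the table layouts, with no new data. It adds 3 scales × 2 visits × 2 areas × 2 regions = 24 n/N cells, plus 3 × 2 × 2 = 12 counts each of Day 71 non-improvers and missing Day 71 ratings. Line 2 will be imprecise: the exact (Clopper-Pearson) 95% interval is 0.8% to 90.6% for 1/3, 0.6% to 80.6% for 1/4 and 0.4% to 64.1% for 1/6. Subjects without a Day 71 rating drop out of line 2.

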4.6. Safety Parameters

4.6.1. Adverse Events

AE verbatim terms as reported by the investigator will be mapped to system organ class (SOC) and preferred term (PT) using the Medical Dictionary for Regulatory Activities (MedDRA). The dictionary version is defined in the Data Management Plan.

4.6.1.1. Treatment Emergent Adverse Events

TEAEs are defined as any AEs that occur or worsen (increase in severity) on the same day or after the study drug administration on Day 1.

Refer to Section [6.3.1.2](#) to identify TEAE status when start date of an AE is unknown.

4.6.1.2. Intensity of Adverse Events

Intensity (or severity) of AEs will be graded as “Mild”, “Moderate” or “Severe”. For AEs with missing severity, the most severe assessment will be imputed for analyses, following worst case principle. If the intensity of an AE changes, then the most severe intensity during the continuous episode will be recorded.

4.6.1.3. Relationship to Study Drug

Causal relationship of an AE with study drug will be classified by the investigator and will be reported as “Not related”, “Unlikely related”, “Probably related” or “Possibly related”. The sponsor will classify “Probably related” and “Possibly related” causality assessments as positive causality and “Not related” and “Unlikely related” causality assessments as negative causality.

Any missing relationship of an AE to study drug will be considered as related to study drug for the analyses, following worst case principle.

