2.3. Risk/Benefit Assessment

Current treatments for EFP have limited efficacy and undesirable side effects. There remains an unmet need for safe and effective nonsurgical therapies to improve the aesthetic outcome in women with cellulite.

The following AEs have been commonly observed in subjects treated with CCH for EFP: local injection site reactions including injection site bruising, injection site swelling, and injection site pain. These events are similar to events reported in the clinical trials of EN3835 for the approved indications. Postmarketing safety data are consistent with safety data reported in clinical trials.

More detailed information about the known and expected benefit, risks, and reasonably expected AEs can be found in the current version of the Investigators Brochure.

Due to the use of the strong magnet, MRI cannot be performed on subjects with any implant containing metal or those who have other internal or external metallic objects as it may cause these objects to move. MRI may potentially increase the temperature of amniotic fluid, so should not be used in pregnant women. The risks associated with punch biopsies include local bleeding and bruising, pain, infection, allergic reaction to the numbing medicine used in the procedure, damage to the structures beneath the skin site (such as an artery or a nerve), and permanent scarring.

All other procedures and activities in this study are generally accepted as standard of care for patients with EFP and do not present any increased risk to the subjects.

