8.3.7. Adverse Events of Special Interest

AESIs for this study include:

- Bruising, ecchymosis, hematomas, and contusions that occur remote to the site of drug administration.
- Any hypersensitivity reactions.
- Local AEs associated with the injection site, including bruising, pain, nodules/mass, ulceration, erythema, pruritus, swelling, and/or induration.

These events will be reported as AEs in the eCRF. All AEs will be evaluated for seriousness and severity. If any of these events meet the criteria for an SAE, they will also be reported as such using the procedure outlined in Section 10.3.

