10.3.2. Relationship to Study Drug

The degree of “relatedness” of the AE to the study medication must be described using the following scale:

- **Not related** indicates that the AE is definitely not related to the study medication.
- **Unlikely related** indicates that there are other, more likely causes and study medication is not suspected as a cause.
- **Possibly related** indicates that a direct cause and effect relationship between study medication and the AE has not been demonstrated, but there is evidence to suggest there is a reasonable possibility that the event was caused by the study medication.
- **Probably related** indicates that there is evidence suggesting a direct cause and effect relationship between the AE and the study medication.

It is the sponsor's policy to consider “Probably related” and “Possibly related” causality assessments as positive causality. “Not related” and “Unlikely related” causality assessments are considered as negative causality.

Assessments will be recorded on the eCRF and must indicate clearly the relationship being assessed. For example, an AE that appears during a placebo run-in phase would be assessed with respect to the placebo treatment received and/or study procedures conducted during this phase. If the AE continued into an active treatment phase, the relationship would be assessed for the active treatment phase only if the AE worsened.

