10.3.4. Reporting Adverse Events and Serious Adverse Events

10.3.4.1. Reporting Adverse Events

Throughout the study, AEs will be documented on the source document and on the appropriate page of the eCRF whether or not considered treatment-related. This includes any new signs, symptoms, injury or illness, including increased severity of previously existing signs, symptoms, injury, or illness. Conditions existing prior to screening will be recorded as part of the subject's medical history. The investigator is responsible for assessing the relationship of AEs to the study medication; relationship will be classified as not related, unlikely related, possibly related, or probably related.

All AEs will be collected by the investigator from the time of signing the informed consent through the Day 265 Visit or for 28 days after the last study treatment in subjects who terminate early. All ongoing AEs must be followed until resolution or until the Day 265 Visit, or 28 days after the last dose of study medication for subjects who terminate early, whichever comes first.

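### AE causality is defined against study drug only and no biopsy-related summary is planned, so the planned AE tables can mix biopsy reactions with CCH reactions

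*SAP*

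**What the plan says.** Causality has one defined object. SAP 4.6.1.3 states: "Causal relationship of an AE with study drug will be classified by the investigator". Protocol 10.3.4.1 agrees: "The investigator is responsible for assessing the relationship of AEs to the study medication". The four-level scale in Protocol 10.3.2 is worded throughout in terms of the study medication. For absent ratings, SAP 4.6.1.3 adds: "Any missing relationship of an AE to study drug will be considered as related to study drug for the analyses".

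The protocol also treats the biopsy as a source of harm in its own right. Section 2.3 says: "The risks associated with punch biopsies include local bleeding and bruising, pain, infection". Protocol 8.2.9 and SAP 3.13.9 have the investigator examine the biopsy site for adverse events caused by the biopsy; the SAP places these examinations at Days 1, 85 and 265. Protocol 8.3.1 follows subjects who were biopsied but not dosed for 28 days after the biopsy. Protocol 9.1 and SAP 3.6 justify 12 subjects partly by the wish to limit exposure to biopsy risk.

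Protocol 8.3.7 lists as AESIs: "Local AEs associated with the injection site, including bruising, pain, nodules/mass, ulceration, erythema, pruritus, swelling, and/or induration". Under Protocol 8.6 and SAP 3.14.2, Dimple 1 is biopsied at screening and never injected. Dimples 2 and 3 are injected at every session and biopsied at Day 71 and Day 251 respectively.

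Protocol 10.3.2 does go a little wider than study drug. It says: "Assessments will be recorded on the eCRF and must indicate clearly the relationship being assessed". Its example, an event in a placebo run-in, would be "assessed with respect to the placebo treatment received and/or study procedures conducted during this phase". This trial has no placebo run-in, and the SAP takes up neither sentence.

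**The concern.** The plan asks the investigator to judge at the visit whether an event comes from the biopsy, but defines no data item or table to hold that judgement. Bruising and pain appear both among the listed biopsy risks and among the local AESI terms, and two of the three biopsies are taken at sites that have also been injected. Two things are at stake. The first is how cleanly the tables describe CCH: a biopsy bruise at an injected dimple can be counted in an AESI or severity row. The second is whether the report counts the harm of an invasive research procedure that the sample size was meant to limit.

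**Working it through.** The plan gives no figure to reproduce on this point, and there is no formal sample size calculation. The check is a reading of the table rules, plus counts and date arithmetic.

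**1. Follow one event through SAP 7.7.2.** Take a bruise at Dimple 2 that starts after the Day 71 biopsy.
- TEAE status: yes, because SAP 4.6.1.1 counts any event from Day 1 dosing onward.
- All-AE and severity tables: counted, with no filter on relationship.
- AESI table: no filter on relationship. The event is counted if it is recorded as a local event at an injection site, and Dimple 2 is one.
- Relationship table, if rated 'Not related' or 'Unlikely related': negative causality, together with every other non-drug cause.
- Relationship table, if the rating is missing: counted as related to CCH.
- Biopsy-related table: none is planned.

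**2. Events before dosing.** SAP 7.7.2 puts events before the first injection into all AE summary tables, whereas Protocol 9.3.3.1 limits summaries to TEAEs. Under the SAP rule, screening-biopsy reactions are pooled too. SAP Table 11 defines the Safety Population by any screening MRI or biopsy, so it includes subjects never dosed. The SAP overview has a row for any drug-related AE, not restricted to TEAEs. An unrated screening-biopsy reaction in a subject who never received CCH would therefore be counted there as drug-related.

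**3. Time from last injection to biopsy.** Day 43 has a window of ±3 (Days 40 to 46).
- Day 71 (+10, Days 71 to 81): nominal 71 − 43 = 28 days; earliest 71 − 46 = 25; latest 81 − 40 = 41.
- The second part of Protocol Table 1 prints ±10 for Day 71. If that applied, the earliest gap would be 61 − 46 = 15 days.
- Day 251 (±15, Days 236 to 266): nominal 251 − 43 = 208 days; earliest 236 − 46 = 190; latest 266 − 40 = 226.
- Protocol 2.2 says injection-site events often resolved within 2 to 3 weeks, that is 14 to 21 days. With the +10 window both later biopsies fall after that period.
- The screening biopsy is at least 14 days before the first dose and at an uninjected dimple, so its pre-dose reactions cannot be CCH reactions.

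**4. Number of biopsies.**
- 12 new subjects: 12 × 3 = 36, of which 12 × 2 = 24 at injected dimples.
- First 7 subjects (Protocol 2.1): 2 had all three doses, so 7 − 2 = 5 had fewer and have only the screening biopsy (Protocol 8.6.2).
- All 19 dosed: at most 19 screening biopsies plus (12 + 2) × 2 = 28 at injected dimples, total 47. If the 2 fully dosed subjects decline, the number at injected dimples is 24.
- These are maxima. Protocol 9.4 stops further biopsies if the interim analysis shows no identifiable change, and withdrawals in the new cohort are not replaced.

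**The case against.** The strongest reply is that biopsy and drug are already separated by time and place. Dimple 1 is never injected, and the later biopsies normally come after injection-site reactions have usually resolved. The existing scale also works: 'Unlikely related' is meant for events with a more likely other cause, and it counts as negative causality. The local AESI is limited to events associated with the injection site, and preferred terms are coded from the investigator's own words, so a biopsy-wound event need not become an AESI. All events are listed by subject, and with about 19 dosed subjects they can be read one by one. Finally, neither the eCRF nor the table shells (SAP Module 2) are among the documents, and Protocol 10.3.2 requires the relationship being assessed to be clear.

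Most of this stands, and it rules out three stronger readings that a reader might infer.
- That biopsy and CCH reactions cannot be separated, or that the trial cannot report biopsy harm. Timing, site examinations, ratings and listings allow this case by case.
- That the eCRF has no procedure item. The documents do not show the eCRF.
- That each misattributed subject moves a rate by 1/19 = 5.3 or 1/12 = 8.3 percentage points. These are not the planned denominators: the Safety Population can include undosed subjects, and AE tables are by region and overall, with no row for the new cohort. A subject counts once per preferred term, so a second event under a term already counted moves nothing.

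The reply does not reach the tables. A 'Not related' rating does not remove an event from the all-AE, severity or AESI tables, and it merges biopsy with all other causes. Attribution that is usually feasible at the visit is better recorded then than rebuilt from listings.

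**Conclusion.** The point holds as a gap in attribution and tabulation. Both documents define causality against study drug alone, and SAP 7.7.2 names no biopsy-related summary. The unfiltered TEAE, severity and AESI tables can therefore mix biopsy-site reactions with CCH reactions, biopsy harm is never counted as such, and unrated events default to CCH, even in subjects never dosed.

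The exposure is up to 36 biopsies in the 12 new subjects, 24 of them at injected dimples. How many reactions would be misplaced is unknown, so no effect on a reported rate is claimed. The conclusion assumes that the unseen eCRF and table shells add nothing beyond the protocol and SAP text; if they already hold a biopsy item and a biopsy table, little remains beyond the missing-causality rule. This is a cheap improvement worth making, not a threat to the primary endpoint.

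**What to change.** - Unless the eCRF already has them, add a relationship-to-biopsy item on the same four levels and, for local events, a site or dimple identifier.
- In SAP 7.7.2, add a table of biopsy-related events, and show local AESIs with and without events judged biopsy-related.
- In SAP 4.6.1.3 and 6.3, limit the missing-causality rule to events with onset on or after the first CCH dose. Protocol 8.3 already dates a worsened baseline condition from the worsening, so such events stay covered. Unrated reactions to the Day 71 and Day 251 biopsies would still default to CCH; the new biopsy item would make them visible.

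The cost is a few extra fields, a mid-study eCRF update with back-entry for the 7 subjects already dosed, and one or two tables. If the eCRF update is judged too costly, the biopsy judgement could be added as a flag in the AE listing at data review, with less assurance than a rating made at the visit.
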